#### **Method:**

The specimen required is 1 mL of blood, collected in a serum separator (gold) tube. The assay is a radioimmunoassay (RIA) performed in the Cleveland Clinic Institute of Pathology and Laboratory Medicine. Results are expected back in 3-6 days. Details are at CCF Guide to Laboratory Services, available on the CCF Intranet at <http://intranet.ccf.org/pathology>.

### 10.2 *Processing of blood for preparation of DNA from leukocytes.*

#### **Rationale:**

DNA sequence differences in the VDR may be useful as a biomarker to predict responsiveness to combination VitD/PDT in individual patients. In the past few years, excitement has been growing about an association between polymorphisms (allelic variants) in the VDR gene and an elevated cancer risk (including breast, prostate, colon, and skin cancer) [20, 21]. Over 300 studies on this topic are now listed in PubMed. Epidemiologic approaches show a strong correlation between VDR polymorphic alleles (named for DNA restriction enzymes that define the altered nucleotide sites) and the risk of melanoma [22] and nonmelanoma [23, 24] skin cancer development. For NMSC, studies have primarily implicated FokI, TaqI, BsmI, and ApaI as potentially important predictors. Overall, the FokI polymorphism is the most interesting, not only because it is very frequently associated with NMSC [24, 25], but also because it is one of the few polymorphisms known to alter VDR levels and function [26]. In their elegant 2001 paper, Whitfield et al. showed that Fok 1 interacts with a second polymorphic site (L/S) which together define a wide range of transcriptional activity of the VDR [31]. FokI detects a single nucleotide substitution (the f allele) in exon II that creates a new translation start site (encoding a protein of 427 amino acids) located three residues upstream from the usual start site (defined by the F allele, and yielding a protein of 424 residues). When 20 different human fibroblast lines were transfected with a VDR-responsive reporter gene ± calcitriol, and each cell line's DNA analyzed to correlate the genotype with VDR transcriptional activity, it was found that ff was the least active genotype, Ff was intermediate, and FF was the most active, over a 7-fold range of

transcriptional activity. The second element of this story involves adenosine (A) repeats in the 3'-UTR of the VDR gene, which vary widely in size between individuals but segregate into a "long" group (L) with 17-24 A's in the repeat, and a "short" group (S) with 10-15 A's in the repeat [31]. The VDR variants with an LL genotype were ~8-fold more active than VDR with a SS genotype. When F/f and L/S alleles were evaluated together, the FF•LL genotype was 10-15 fold more active than the f/f•SS genotype. We plan to perform genotyping of our patients' DNA to determine the status of the F/f and L/S alleles, and to correlate these findings with therapeutic responsiveness to ALA-PDT, ± D3 supplementation.

As an alternative (or additional) assay, we plan to look at single nucleotide polymorphisms (SNPs) in CYP27B1, the 1 $\alpha$ -hydroxylase enzyme that regulates 1,25diOH-D3 production. According to a study from the group at Univ. Arizona, four SNP variants of CYP27B1 (R107H, V166L, S356N, and V374A) show markedly reduced 1 $\alpha$ -hydroxylase activity, while one variant (V166L) shows increased activity. The presence of these allelic variants will be established by qPCR, to see whether they correlate with responsiveness to PDT.

#### **Method:**

The complete procedure for extracting blood for leukocyte DNA preparation is given in Appendix 1.

Briefly, blood will be collected in a 10 mL lavender top Vacutainer tube with EDTA. The phlebotomist in the outpatient Crile A61 will call [name] technician/designated staff to inform him/her that a specimen is waiting; the technician will then pick up the sample and transport it to [name] lab. The blood should stay at room temperature, and NOT be put on ice (which would activate platelets). A simple and reliable kit from Qiagen will be used to prepare the DNA. The first step involves adding a solution to lyse the cells and precipitated the proteins; after this stage, the tube can safely remain at room temperature for weeks prior to DNA extraction (see Appendix 1).

The analysis of DNA sequences using polymerase chain reaction (PCR) is a standard procedure in [name] laboratory. We will employ published DNA primer sequences, described in the publications listed in the Rationale for (B) given above.

#### **Safe storage of the patient samples**

- [Describe where samples will be stored, maintained and for how long.](#)

DNA samples will be stored in a locked minus 80 degree ultrafreezer, in [name] laboratory (room ND4-25A in the Lerner Research Institute). The samples will be maintained for up to 10 years.

- [Will samples contain subject identifiers or are names replaced with codes and a separate key?](#)

Blood sample tubes and data sheets in the laboratory will be labeled with a code consisting of the first 5 digits of the patient's 8-digit MRN along with the date that the phlebotomy was performed (i.e. the date of the blood draw). This should ensure anonymity of the data while preventing mistakes when linking the laboratory results to the correct patient. Study personnel with password-protected access to the database registry will use the code to unequivocally

identify the subject's file within the Oracle database and thereby enter the subject's laboratory results into the proper data field.

### **Procedure (C): Correlation of biomarker results to clinical outcomes (Database Registry)**

Clinical parameters will be extracted from the EPIC electronic medical record, for each study patient, at the treatment visit and the 3 month follow-up. The data fields to be used in this study are identical to items already IRB-approved in our established PDT database (IRB 09-953), with the exception that we have added 4 new fields to capture results of the Vitamin D tests and biomarker results. This strategy will allow us to eventually add clinical parameter data from this study into the larger comprehensive database, but the biomarker data will continue to reside separately in the study-specific database.

**Privacy and confidentiality:** Medical information obtained in this study will remain in the Oracle-based database registry within the Department of Dermatology. Information contained in this database is confidential and can only be viewed by investigators and study staff who have password access. Data from the assays conducted in [name] laboratory will be de-identified on all tubes, vials, and notebooks through use of the coding system described in the previous paragraph. Again, investigators with password-protected access to the database will be the only people able to break the code when the time comes to interpret the results (to correlate lab results with clinical outcomes for individual patients).

- [Describe how subjects may withdraw the use of their samples.](#)

The Informed Consent document informs the subject that he/she can withdraw permission for use of their samples at any time, and explains how to do this by contacting the Principal Investigator (PI) in writing.

- [Will any samples or research data be given to external sponsors or other 3rd parties?](#)

No.

- [Will any genetic testing be undertaken \(i\), and shared with subjects \(ii\)?](#)

(i) Yes; (ii) No.

The genetic sequence of very specific loci in genes that encode the Vitamin D receptor (VDR), and in the genes for 1-alpha-hydroxylase and thymidine synthase (enzymes which metabolize Vitamin D and 5-fluorouracil respectively), will be examined for the specific purpose of asking whether the presence of a particular variant statistically correlates with PDT treatment outcomes. There are no known diseases that are associated with these vitamin D enzymes nor the TS promoter variants. Therefore, because no known information with the potential to cause harm exists within the limited DNA sequences to be examined, we have no plans to share any DNA sequence information with the subjects. However, the Informed Consent will instruct subjects that they are free to withdraw permission for use of their DNA data at any time by contacting the PI in writing.

## **11.0 STUDY PARAMETERS AND DETAILED STUDY CALENDAR**

Each step of the study has been described in detail under Section 6.0, “Treatment Plan”. Each study visit, and events occurring between visits, are laid out in the Table in section 11.6 (“Calendar”).

**Allowances for variations in scheduling:** A visit window of **3 months** is allowed when scheduling the final follow-up assessment visit.

In brief, the study consists of the following activities:

### **11.1 Initial evaluation and screening (Visit 1)**

Initial exam, and review of previous records; blood draw for 25-OH-D3 levels (and leukocyte DNA, for VDR receptor analysis). Vitamin D study pills will be given to the patient.

11.2 **At home:** Study nurse will call patient to instruct patient on when to start Vitamin D supplementation.

### **11.3 PDT treatment (Visit 2)**

All AK lesions are measured clinically and photographed. Noninvasive fluorescence dosimetry may be performed on up to 6 lesions. *Levulan KerastickTM* will be applied to each lesion and left to incubate for 30 minutes. **Blue light** (Blu-U device, 20 J/cm^2, 33 minutes) will be administered.

11.4 **At home:** Study nurse will call patient to check up on the patient and record side effects at 24-48 h.

### **11.5 Final observation (Visit 3)**

At month 3, the subject will return for final exam and photography of lesions.

11.6 **Calendar.** (Please see next page for **STUDY CALENDAR**)

**CALENDAR. Timeline of procedures for patients enrolled in the study.**

**Yellow:** Clinic visits. **Gray:** events taking place at home. **Green:** steps that are critical to decision-making.

	VISIT 1 No PDT	Start VD	VISIT 2 PDT 1	Phone Call	VISIT 3 No PDT
Scheduled visit: → Procedure: ↓		5 d or 14 d before PDT	Day 0		Month 3 *
Review previous clinical records	X				
Blood draw	X				
Dispense Vitamin D3	X				
Call, and tell the patient to start taking pills		X			
Pill Count (verify patient took pills)			X		X
Skin exam and lesion counts	X		X		X
Photograph lesions			X		
Topical ALA application			X		
Measure PpIX fluorescence on selected lesions at 30 minutes			X		
Blue light exposure (20 J/cm  )			X		
Phone call to patient, to record side effects at 24-48 hr post PDT				X	

\*Time window for scheduling Visit 3 will be 3-6 months after Visit 2, to match the protocol of the control group (IRB 16-1615).

## **12.0 MEASUREMENT OF EFFECT**

### **12.1.1 *To establish a diagnosis of AK.***

AK will be diagnosed through a combination of touch and visual inspection.

## **12.2 Methods for Evaluation of AK Response**

### **12.2.1 *Number of AK Lesions Measured from Clinic Visits and Photographic Images***

(Primary Objective)

Percent reduction of actinic keratoses at a 3-month follow-up visit will be used to evaluate the overall outcome of PDT with prior Vitamin D supplementation. This will be achieved by counting AK lesions at visit 2 and visit 3.

### **12.2.2 *Noninvasive fluorescence measurements (NIF) of lesions***

(Secondary Objective)

The *maximal levels of PpIX*, measured 30 minutes after Levulan application at each treatment session, will indicate the degree of accumulation of porphyrins in the areas of skin with actinic damage.

### **12.3 *Tolerability and patient satisfaction***

(Secondary Objective)

We will collate the results from the patient symptom score sheets filled out by each patient in the week following each PDT treatment. We will also record erythema (on a scale of 1 to 4+), from clinical exam and from the photographs, in the treated areas just prior to the second treatment in each PDT cycle. The absence/presence of pain will be recorded on a 0-to-10 visual/analog scale.

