**Figure 5. Study Design.**

At **Visit 1**, patients will be given oral D3 to take for either 5 days or 14 days (according to their normal or deficient 25OH-D3 level, respectively) prior to the PDT treatment at **Visit 2**. Mandatory F/U visit at 3 months (**Visit 3**). After that, patients will be followed clinically every 6-12 months.

Study patients will have three mandatory visits. At Visit #1, patients will sign the ICF and have their blood drawn. A vitamin D-relevant history will be taken, and CIS lesions counted by a clinician. The patient will be given enough D3 pills (10,000 IU each) to be taken daily at home, beginning at either day -5 or day -14, as per their assignment (see above). At Visit #2, to assess how much PpIX is generated in the skin, ten lesions will be measured using our fluorescence probe dosimeter (before and after ALA application). PDT will then be performed. At Visit #3 (which is 3-6 months after PDT), the patient's lesions will be counted to assess the treatment response).

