## **6.0 TREATMENT PLAN**

**6.1. VISIT 1:** As part of the Informed Consent process, the patient will be seen in the clinic for a full screening visit (**Visit 1**), including a review of medical records and a physical exam. Informed Consent will be obtained on-site. AK lesions will be carefully evaluated to determine if the patient meets eligibility criteria (> 10 AK lesions). A study nurse from the CRU will draw two tubes of blood, one for serum D3 assay, the other for leukocyte collection (buffy coat) and preparation of DNA. The patient will be sent home after scheduling the date of the next visit, in approximately 1 month.

**Evaluation procedures at Visit 1:** Blood will be collected in two tubes: one with an anticoagulant (e.g. heparin) and the other without. The nonheparinized tube will be sent to CCF Clinical Laboratory Medicine for routine measurement of vitamin D (calcidiol) serum levels. The heparinized tube will be transported to [name] laboratory for preparation of leukocyte DNA (see Procedure B).

**VISIT 2: Treatment procedure:** The patient will return on the treatment day, and all AK lesions will be carefully marked with a water-soluble pen, photographed and mapped. PDT will then be conducted as per our routine procedure, as follows. The prodrug (5-aminolevulinic acid, 5-ALA; Levulan® Kerastick™, 20% Topical Solution) is applied to the entire involved area of skin, allowed to dry, and left on the skin surface for a period of time between 15 to 30 min (for AK of the face and scalp). During that time, the 5-ALA prodrug is selectively absorbed by preneoplastic cells and is converted within the cells' mitochondria into protoporphyrin IX (the molecule that constitutes the actual phototarget). The patient is positioned under the light source (Blu-U, 400 nm wavelength), wearing protective yellow goggles, and is illuminated for 30 min. Upon completion of PDT, aftercare steps are explained to the patient, and then the patient is sent home with emollient samples and written aftercare instructions. A questionnaire of side effects during the 6 days post-PDT will be filled out at home.

**Visit 3: Final evaluation visit (3 months post-PDT):** AK lesions will be counted and photographed.

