### **6.3 Duration of Follow Up**

Patients will be followed for 3 months, as specified in the study Calendar; **section 11.0**. The single treatment will occur at Visit 2, at 3 months prior to the last visit. No formal study follow-up is planned after completion of 3 months, but every effort will be made to encourage patients to return at 6 month intervals for 2 years for routine examination, at which time will document AK status (clearance/recurrence) in our PDT database registry, and provide additional standard-of-care as needed.

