#### **8.1.2 *Photodynamic Therapy***

When ALA is converted into PpIX in tumor cells, and illuminated with light, the following signs and symptoms are known to occur as part of the therapeutic response:

- (i) Stinging and/or burning sensation: >50%
- (ii) Erythema (localized redness): 35%
- (iii) Edema, localized: >35%
- (iv) Peeling, transient: <50%
- (v) Blister formation: rare

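### The 1-to-4+ erythema grade in Section 12.3 is timed to a second PDT treatment that the single-PDT design does not contain, so this part of the tolerability endpoint yields no grades.

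*Combined protocol and SAP*

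**What the plan says.** Section 12.3 (tolerability and patient satisfaction, labelled a secondary objective) has three parts. It collates symptom sheets that patients complete in the week after PDT. It grades redness: "We will also record erythema (on a scale of 1 to 4+), from clinical exam and from the photographs", with the timing given as "in the treated areas just prior to the second treatment in each PDT cycle". It also records pain on a 0-to-10 scale.

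The treatment schedule is set out elsewhere:

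- Section 6.3: "The single treatment will occur at Visit 2, at 3 months prior to the last visit".
- Section 3.1, text with Figure 5: "Study patients will have three mandatory visits".
- Section 11.6 calendar: one PDT column, with Visits 1 and 3 marked as having no PDT. Its footnote reads "Time window for scheduling Visit 3 will be 3-6 months after Visit 2".

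Two remote contacts follow PDT. Section 6.1 says "A questionnaire of side effects during the 6 days post-PDT will be filled out at home", and the calendar has the row "Phone call to patient, to record side effects at 24-48 hr post PDT". Section 8.3 separately asks for a toxicity grade on CTCAE version 4.0 for every adverse event. Section 14.0 lists tolerability as a secondary objective, gives only pain scale measurements as its content, and does not mention erythema.

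**The concern.** The erythema measure is fixed to an event that the schedule does not contain. Nobody following 12.3 literally could make the assessment, and the calendar has no erythema row to fall back on.

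The local reaction matters to this trial's own hypothesis. Section 2.0 proposes that vitamin D3 raises PpIX in the lesions and so increases photoactivation. A stronger skin reaction is a foreseeable consequence of that mechanism, although the protocol does not say so; this is an inference. The protocol does treat post-PDT redness as relevant: 8.1.2 lists it among the known reactions, and 4.2.3 excludes users of topical retinoids because of it. Section 2.2 expects the results to support the combination as safe.

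At stake is whether a tolerability statement would rest on a redness grade collected in the same way from every patient. An acute reaction that was not graded at the time cannot be graded at month 3.

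**Working it through.** The plan gives no figure to reproduce on this point. The check sets 12.3 against the schedule.

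**Step 1: does the time point exist?** PDT treatments per patient = 1 (Sections 6.3 and 11.6). Second treatments = 1 - 1 = 0. With 30 patients, grades obtainable under the 12.3 timing = 30 x 0 = 0.

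**Step 2: could another scheduled contact supply the same grade?**

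| Contact | Timing | What is scheduled | Can it give the 12.3 grade? |
|---|---|---|---|
| Visit 1 | Before PDT | Records review, blood draw, lesion count | No: before PDT |
| Visit 2 | Day of PDT | Lesions marked, photographed and mapped, then ALA and light (6.1) | No: exam and photographs precede illumination, and no later ones are described |
| Phone call | 24-48 h after PDT | Side effects recorded (11.4, 11.6) | No exam or photograph; no redness item or scale shown |
| Home questionnaire | 6 days after PDT | Side effects (6.1); not in the 11.6 calendar | No exam or photograph; no redness item or scale shown |
| Visit 3 | 3-6 months after PDT | Lesion count; photographs per 6.1 and 11.5 | No: months after the reaction |

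All three mandatory visits are accounted for by screening, PDT and final assessment. Clinic visits after PDT and before month 3 = 3 - 3 = 0.

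**Step 3: is a second session implied anywhere?** The calendar labels its PDT column as number 1, and the table of contents calls Visit 2 the first treatment. No second session is scheduled in Sections 3, 6 or 11, and 6.3 calls the treatment single. The labels do not create a time point.

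**Step 4: is the measure rescued in the statistics section?** No. Section 14.0 does not name erythema under tolerability and gives no alternative timing for it.

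**The case against.** The strongest reply is that this is leftover wording from a multi-treatment design and that redness is not lost. Much of that stands. Section 12.3 itself begins with symptom sheets from the week after PDT, plausibly the same form as the 6-day questionnaire. The 24-48 h call records side effects. Section 8.3 requires every adverse event, whether observed or reported, to be recorded with a CTCAE grade.

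Two stronger readings are therefore tempting and are not supported.

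- A reader might infer that erythema is never recorded in this trial. The documents do not show that. There are at least three routes by which redness can reach the data, and one carries a grade. Neither the symptom sheet nor the questionnaire is reproduced, so it cannot be assumed that they omit redness.
- A reader might apply the 35% erythema rate in 8.1.2 to 30 patients (0.35 x 30 = 10.5) and conclude that 10 or 11 patients would have ungraded erythema. That does not follow. The 35% is a general PDT reaction rate with no link to the 12.3 time point, and redness reported as an adverse event would receive a grade under 8.3.

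It is also fair to say that Section 14.0 makes pain the tolerability measure, so erythema is one component of a secondary endpoint.

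What the reply does not remove is the failed rule. Adverse event reports depend on what is observed or volunteered, and the call and questionnaire have no documented redness scale. None of them guarantees one comparable grade per patient, which is what 12.3 set out to collect.

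**Conclusion.** The point holds for the graded measure in 12.3: it has no valid time point and gives 0 grades in 30 patients. This is a stated rule that cannot be carried out, rather than a missing detail. It affects one component of a secondary tolerability endpoint. The lesion-count comparison between Visits 2 and 3, which is the primary endpoint, is untouched, and redness may still be captured less systematically.

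The conclusion assumes that the single-PDT schedule in Sections 3, 6 and 11 is the intended one and that no post-illumination exam or photograph is planned beyond what is written. How much redness information would survive through the other routes cannot be quantified, because the forms are not in the documents. The correction is worth making because it is cheap and must be in place before patients pass Visit 2 to be of use.

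**What to change.** In Section 12.3:

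- Delete the timing part of the erythema sentence (the reference to a second treatment in a cycle) and the words that name exam and photographs as the source.
- Replace the reference to each treatment with the single PDT at Visit 2.
- Define erythema as a patient-reported redness grade on a stated scale, including how no redness is scored, since the present scale starts at 1. Take the worst grade over the 24-48 h call and the 6-day home questionnaire as the measure.

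Add that redness item to both instruments; the documents do not show that either has one now. Add a questionnaire row to the 11.6 calendar. Compare with the historical controls only on items that IRB 16-1615 collected at the same times, because the documents do not say what side-effect data that study holds.

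If the item is not added, remove erythema from 12.3 and make no graded erythema claim in the report.

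The cost is protocol and form wording plus one item on two planned contacts, with no new visit. The price in quality is that erythema becomes patient-reported instead of clinician-graded.
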